STUDY ENDPOINTS	
Primary endpoint:
 
• Cross clamp time 
Secondary endpoints:
 
• Cardiopulmonary bypass time• Device technical success (defined as the successful delivery and deployment of a registry valve and delivery system and subject leaving the operating room with valve in place)• First Attempt Success Rate• ICU and Hospital Length of Stay• Hemodynamic performance (mean gradient, peak gradient, effective orifice area [EOA], EOA index, performance index, cardiac output [CO], cardiac index [CI], valvular regurgitation [including paravalvular leak] confirmed by an Echocardiographic Core Laboratory) at Discharge and 6 months (if available) 
Patient related endpoints:
 
• NYHA functional class compared to baseline• Change in Quality of Life questionnaire SF-36 and EQ-5D from Baseline to 6 months (if available)• Fitness for hospital Discharge
------------------------	---

	
Safety endpoints:
 
Complication rates at 30 days (early rates) and at 6 months :
 
• All cause mortality
◦ Study valve-related mortality• Thromboembolism
◦ Stroke◦ TIA◦ Non cerebral embolism• Valve Thrombosis• Major Bleeding event• Endocarditis (study valve)• Structural valve deterioration• Non Structural valve deterioration
◦ Paravalvular Leak minor◦ Paravalvular Leak major◦ Other non SVD• Hemolysis• Reoperation
◦ Trial valve reoperation• Study valve explants• Implant-related new or worsened cardiac conduction disturbance requiring permanent pacemaker implant• Renal Failure• Respiratory Failure• Deep Sternal Wound infection 
The Clinical Events Committee (CEC) will adjudicate the adverse events including adverse events resulting in death as outlined in their charter and adjudicate these events for their relatedness to the investigational device, and the investigational device procedure.

--	--

2. Introduction

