Potential risks associated with aortic valve replacement surgery include:

- Allergic reaction
- Annular dissection
- Aortic or arterial dissection
- Asystole and/or cardiac arrest
- Bleeding
 - Peri or post-procedural
 - Anticoagulant related
 - Pericardial tamponade
 - Hematoma
 - Cerebral vascular
- Cardiogenic shock
- Disseminated intravascular coagulation (DIC)
- Embolism, pulmonary
- Esophageal tear/rupture
- Heart failure
- Hypo- or hypertension
- Hypoxemia
- Infection: local, wound or systemic
- Infection Septicemia: bacterial, viral, fungal
- Myocardial infarction
- Myocardial perforation, free wall
- Multi-system organ failure (MOF)
- Pericardial effusion
- Pleural effusion
- Pulmonary edema
- Pneumonia
- Renal failure, acute
- Respiratory failure
- Thrombocytopenia, (Non-HIT)
- Thrombocytopenia, heparin induced (HIT)
- Thromboembolism
 - Venous, peripheral or central
 - Arterial, peripheral or central
 - Pulmonary, thrombus or other

In addition to the above, the following are potential risks that could be uniquely associated with the EDWARDS INTUITY Elite Valve System:

- Trauma to the mitral chordae resulting from the delivery system
- Frame damage or under-flaring resulting in a reduction of effective orifice area
- Loss of frame structural integrity resulting in damage to aortic wall or aortic annulus
- Frame expansion resulting in conduction interruptions or disturbances (i.e. arrhythmia)
- Frame expansion resulting in mitral valve impingement or abrasion with or without mitral regurgitation
- Insufficient frame expansion resulting in perivalvular leak requiring intervention or reoperation

Some or all of these risks may require reoperation, valve explantation, or may lead to permanent disability or death. All events related to the registry medical procedure or the valve and any post-operative cardiac related events will be collected and reviewed throughout the registry duration and follow-up period. Investigators will be notified of any additional risks identified during the registry that could affect the health, safety or welfare of the subjects in the investigation.

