6. REGISTRY OBJECTIVES

Primary Objective:

- To describe procedural time (Cross Clamp Time) and to compare the Cross Clamp Time collected with EDWARDS INTUITY Elite in this registry to the largest published dataset with conventional valves within the MIS setting (Merck et al ²¹). The published dataset will be used as a control group.

Secondary Objectives:

- To describe short term (30 days) and long term (6 months) clinical safety
- To assess and compare hemodynamic data with EDWARDS INTUITY Elite to a conventional valve at discharge and at 6 months post AVR
- To assess Quality of Life at baseline, and at 6 months post AVR
- To assess NYHA functional class at baseline, discharge and at 6 months post AVR
- To assess Fitness for hospital discharge

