Major Paravalvular Leak	
Major Paravalvular Leak is any paravalvular leak, exclusive of that associated with thrombosis or infection, that leads to intervention or re-operation (with or without symptoms), or that is graded 3+ or greater (with or without symptoms and with or without intervention/ re-operation), or that results in death, or that is 3+ or greater when diagnosed by autopsy.

Major Bleeding	
Major bleeding is bleeding that causes death, hospitalization, or permanent injury (e.g. vision loss) or requires transfusion of 3 or more units of PRBCs.
 
Major bleeding unexpectedly associated with minor trauma should be reported as a bleeding event, but bleeding associated with major trauma or a major operation should not.
 
Minor Trauma examples are subdural hematoma, IC bleed associated with fall, hematuria from catheter
 
Major Trauma/Major Operation examples are a fracture, CT surgery. These will be noted but do not count as events for the analysis.
 
All bleedings requiring hospital admission such as an admission for GI Bleeding, Access Site Hematoma or other source of bleeding should be reported as Major Bleeding.

Reoperation (on the registry valve)	
Re-intervention is any surgical or percutaneous interventional procedure that repairs, otherwise alters or adjusts, or replaces a previously implanted prosthesis or repaired valve (registry valve). In addition to surgical reoperations, enzymatic, balloon dilation, interventional manipulation, repositioning, or retrieval, and other catheter-based interventions for valve related complications are also considered re-interventions. Indications for re-interventions must be reported. Open surgical and percutaneous catheter re-interventions should be listed separately.
 
An explant is defined as a re-intervention resulting in removal of the implanted valve after the patient leaves the operating room with an implanted valve, after the index procedure.

Renal Failure	
An acute event or worsening of renal function resulting in one or more of the following: 1) Increase of serum creatinine to >2.0 mg/dL, and 2x most recent preoperative creatinine level. 2) A new requirement for dialysis postoperatively

Respiratory Failure with need for mechanical ventilation (Post index procedure)	
Respiratory event requiring endotracheal reintubation and ventilator support post index procedure.

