12.3. SAFETY DATA

- All cause mortality
 - Study valve-related mortality
- Thromboembolism (Stroke, TIA, and Non cerebral embolism)
- Valve Thrombosis
- Major Bleeding event

- Endocarditis (study valve)
- Structural valve deterioration
- Non Structural valve deterioration
 - Paravalvular Leak minor
 - Paravalvular Leak major
 - Other non SVD
- Hemolysis
- Reoperation
 - Trial valve reoperation
- Study valve explants
- Implant-related new or worsened cardiac conduction disturbance requiring permanent pacemaker implant
- Renal Failure
- Respiratory Failure
- Deep Sternal Wound infection

Early adverse events within 30 days of procedure will be reported as the number of events divided by the number of enrolled subjects. Linearized rates will be used to summarize adverse events for the late (>30 days) post-operative period. The linearized rates will be calculated as the number of late events divided by the total number of late-subject years.

Percentages for the early events and linearized rates for the late events also will be calculated for all other complications observed in the trial.

Actuarial rates based on the method of Kaplan - Meier will be calculated for each of the safety endpoints at thirty days and six months; the number of subjects at risk for death will be reported at each of these intervals.

On top of Implant-related new or worsened cardiac conduction disturbance requiring permanent pacemaker, the counts and percentage of subjects who experience new or worsening cardiac rhythm or conduction disturbances will be calculated at each follow-up visit. The identification of “new and worsening” cardiac rhythm or conduction disturbance will be based on a comparison to the previous visit.

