18.3. APPENDIX C: Registry Definitions

Device Explant - Explant is defined as a re-intervention resulting in removal of the implanted valve after the patient left the operating room with an implanted valve, after the index procedure

Device Deficiency - Inadequacy of a medical device with respect to its identity, quality, durability, reliability, safety or performance. **NOTE:** Device deficiencies include malfunctions, use errors, and inadequate labeling.

Device Removal - The excision of the investigation bioprosthesis before the EDWARDS INTUITY Elite Valve System procedure was completed. The heart *was not* restarted with the bioprosthesis implanted. Patient still IN the operating room.

EDWARDS INTUITY Elite Valve Device Technical Success - The successful delivery and deployment of a registry valve and delivery system and subject leaving the operating room with valve in place.

EDWARDS INTUITY Elite Valve Procedural Success - is defined as device technical success followed by the absence of adverse events requiring device reoperation, requiring implantation of permanent pacemaker (with baseline sinus rhythm and no other conduction issues), or subject death, within discharge or 10 days post index procedure whichever comes first.

Enrollment cohort:

A subject will be considered enrolled into the registry when he/she has signed the informed consent, met all the registry eligibility criteria.

Implant failure - is defined as a re-intervention resulting in removal of the implanted valve with the patient still in OR, after the index procedure

Index Procedure - Surgical replacement of the aortic valve.

New York Heart Association Classification

- Class I: Patients with cardiac disease but without resulting limitations of physical activity.
- Class II: Patients with cardiac disease resulting in slight limitation of physical activity. Patients are comfortable at rest. Ordinary physical activity results in fatigue, palpitation, dyspnea, or angina pain.
- Class III: Patients with cardiac disease resulting in marked limitation of physical activity. They are comfortable at rest. Less than ordinary physical activity causes fatigue, palpitation dyspnea, or angina pain.

Class IV: Patients with cardiac disease resulting in inability to carry on any physical activity without discomfort. Symptoms of cardiac insufficiency or of the angina syndrome may be present even at rest. If any physical activity is undertaken, discomfort is increased.

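### The Major Bleeding definition excludes bleeding tied to a major operation and does not exempt the index valve operation, so the 30-day rate can omit such bleeding without saying so

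*Combined protocol and SAP*

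**What the plan says.** Section 11.2, Table 2, sets the severity threshold: "Major bleeding is bleeding that causes death, hospitalization, or permanent injury (e.g. vision loss) or requires transfusion of 3 or more units of PRBCs". The same row then separates two situations. Major bleeding that unexpectedly follows minor trauma is reported as an event; bleeding that goes with major trauma or a major operation is not. The row illustrates the second group and states the consequence: "Major Trauma/Major Operation examples are a fracture, CT surgery. These will be noted but do not count as events for the analysis". It closes by saying that every bleed needing a hospital admission is to be reported as Major Bleeding, with gastrointestinal bleeding and access-site hematoma among the examples.

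Appendix C defines the index procedure as "Surgical replacement of the aortic valve". The synopsis lists major bleeding under "Complication rates at 30 days (early rates) and at 6 months", and Section 12.3 gives the early formula: "Early adverse events within 30 days of procedure will be reported as the number of events divided by the number of enrolled subjects". Section 9.4 starts adverse event collection when the subject is in the operating room. Section 4.1 lists bleeding among the risks of the surgery, with "Peri or post-procedural" as its first sub-item.

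**The concern.** Every subject who receives the registry valve has just had a major cardiac operation, so in the first 30 days much of the bleeding that could meet the severity threshold may be bleeding from that operation. If the exclusion is applied as written, those bleeds leave the numerator of the early rate even when they meet the limit "requires transfusion of 3 or more units of PRBCs".

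A secondary objective in Section 6 is "To describe short term (30 days) and long term (6 months) clinical safety". A reader of the 30-day table would take a row headed Major Bleeding to include surgical bleeding, because nothing on the row says otherwise. Section 2.1 cites less blood loss and less transfusion as advantages of the minimally invasive approach, and Section 2.2 says the data will support publications and marketing information. An early bleeding rate with an unstated exclusion is therefore open to misreading. The same definition feeds the Kaplan-Meier estimates for each safety endpoint at 30 days and six months in Section 12.3.

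**Working it through.** The plan states no bleeding rate, so there is no figure to reproduce. The check is a comparison of texts.

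1. **Does the exclusion reach the index operation?** Table 2 excludes bleeding associated with a major operation and gives CT surgery as an example. CT is missing from the abbreviation list in Appendix B, so reading it as cardiothoracic is an inference. It is the natural one: the term illustrates an operation, and the stroke definition in the same table writes computed tomography in full. Even without the example, aortic valve replacement is a major operation.

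2. **Is there an exemption elsewhere?** None was found in the bleeding row, in Section 12.3 or in Appendix C. Other rows of Table 2 do address the index operation: embolism counts from anesthesia onward, intraoperative myocardial infarction is expressly not counted, and respiratory failure is limited to the period after the index procedure. The bleeding row has no comparable rule.

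3. **Is the row consistent with itself?** Two cases:
   - *Readmission for bleeding from the index operation.* The closing sentence counts it; the major-operation sentence excludes it. The row gives no order of precedence.
   - *Bleeding during the index stay.* The patient is already in hospital, so the admission sentence does not bring the bleed back. The major-operation sentence applies and the bleed is not counted.

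4. **Effect on the early rate.** Section 12.3 computes

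   early rate = events within 30 days / enrolled subjects.

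   If E_other is the number of countable bleeds unrelated to an operation and E_index the number of qualifying index-operation bleeds in the index stay, the literal rule reports E_other / N, while a reader may expect (E_other + E_index) / N. The difference is E_index / N.

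5. **Scale, by assumption only.** With N = 300 (the planned maximum in Sections 12 and 12.5) and an assumed share p of subjects with one such bleed, the number omitted is 300 × p:
   - p = 0%: 300 × 0 = 0
   - p = 2%: 300 × 0.02 = 6
   - p = 5%: 300 × 0.05 = 15
   - p = 10%: 300 × 0.10 = 30

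   None of these shares comes from the documents. They show only how a given share translates into events.

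**The case against.** The strongest reply is that the exclusion was never aimed at the index operation. It stands in contrast to minor trauma such as a fall, and its companion example is a fracture, so it can be read as covering bleeding explained by some later, unrelated event. The 3-unit transfusion criterion and the access-site hematoma example also pull toward counting procedural bleeding. This is a fair reading and may be what was intended. It does not remove the problem, because the text does not say so and the general wording covers the index operation.

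Two stronger conclusions are tempting, and the documents support neither. A reader might infer that the 30-day rate would be close to zero by design. It would not: gastrointestinal and anticoagulant-related bleeding, bleeding after minor trauma, and other qualifying bleeds not tied to an operation still count. A reader might also infer that the excluded bleeds are never analysed. That goes too far as well. Fatal bleeds are in all-cause mortality, and Section 12.3 provides percentages for all other complications seen, where noted bleeds might appear. Valve-related mortality includes deaths caused by a bleeding event, although the plan does not say whether an excluded bleed qualifies there.

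The Clinical Events Committee adjudicates endpoints and potential endpoints, and its charter may contain a rule on this; the charter's content is not in the documents. Finally, bleeding is one of many descriptive safety endpoints, and the only hypothesis test concerns cross-clamp time. All of this limits the consequence. None of it puts index-operation bleeds into the Major Bleeding rate or marks that rate as excluding them.

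**Conclusion.** The point holds as a gap in definition and labelling. Taken literally, the Major Bleeding row allows the 30-day rate to omit qualifying bleeding from the index operation during the index stay, and it gives contradictory instructions for readmissions. The conclusion rests on the general term major operation covering aortic valve replacement, which does not depend on how CT is expanded, and on the absence of any exemption in the text.

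The size of the omission cannot be estimated from the documents. It is zero if no index-operation bleed meets the threshold, or if the committee's charter already counts such bleeds. The primary endpoint and its power are unaffected. This is a low-severity point and an inexpensive one to settle.

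**What to change.** In Table 2, state whether the major-operation exclusion covers the index valve operation, and reconcile that statement with the sentence on hospital admissions so that a readmission for index-operation bleeding has one classification.

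If index-operation bleeding is to be excluded, keep the existing endpoint and make two changes to the early table in Section 12.3:
- label the current row *Major bleeding, excluding index-operation bleeding*;
- add a row *Major bleeding associated with the index operation*, with the same severity limits, adjudicated by the Clinical Events Committee from the bleeds already noted.

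If it is to be counted, the clarifying sentence in Table 2 is enough.

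The cost is one more table row and an early safety table that looks less favourable. Units of packed red cells must also be recorded with each noted bleed. Neither the operative list (Section 9.6.1) nor the discharge list (Section 9.7) names transfused units, but the existing 3-unit criterion already needs them.

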In the operating room, the intra-operative exclusion criteria will be assessed by careful examination of the valve anatomy, valve condition and associated structures. Any other intra-operative exclusion criteria or eligibility exclusion criteria may be assessed throughout the procedure.

Adverse events for enrolled patients are collected from the time the subject is in the operating room.

Enrolled patients, due to an intra-op Exclusion criteria can be excluded (defined as intra-op screen failure). The reason for ineligibility will be explained to them and will be documented into the eCRF. Subjects will then be followed by their primary health care provider per best medical practice.

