9.7. Hospital Discharge

The clinical evaluation and data requirements for the registry subjects at the time of hospital discharge:

- Fitness for hospital discharge

- **Length of stay:** Total length of stay in hospital and duration in ICU
- **Disposition at hospital discharge:** home, rehabilitation unit
- **Adverse Events:** Post-operative procedure or cardiac related events that resulted in medical or surgical intervention; all other serious adverse events per investigators decision using the available adverse event code list will also be collected
- **Medical examination:** NYHA classification, weight
- **ECG 12 lead**
- **Echocardiography data will be collected (if available) and CD will be sent to CoreLab**
- **Anticoagulation therapy**
- **Coagulation profile, if patient is being treated with a coumadin derivation medication (INR and PT)**
- **Blood Studies: RBC, WBC, HGB, HCT, Reticulocytes, Platelet counts, Serum Creatinine (if available per standard of care)**

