9.8. Follow-up Visits Registry Procedures

9.8.1. FOLLOW-UP VISIT WINDOWS

Post-procedure clinical evaluation will be performed on all enrolled subjects at 30-days and 6-months post-implant date. Follow-up at 30 days- will be conducted by phone. All follow-up data will be documented on the CRF.

Patient assessments will be done according to the sites standard of care.

It is important that the follow-up visit schedule is maintained as closely as possible for all subjects. Edward's recognizes that subjects may not be able to return for all scheduled visits at precisely the date required, and therefore, an acceptable window of time for the 30 day follow-up period is described in Table 1. Registry visits should be scheduled as close to the earliest portion of the window for the follow-up period so that cancellations and visit rescheduling can still be conducted within the required time period.

TABLE 1. SCHEDULED FOLLOW-UP VISIT DAYS AND APPLICABLE VISIT WINDOWS

Visit	Visit Window days	Timing from Implant (Day 0)
Screening		Day -30 to Day -1
Discharge		Post-op - Day of Discharge
POD 30	+/- 7	Day 23 to Day 37
POD 180 (if applicable)	+/- 45	Day 135 to Day 225

Protocol required registry follow-up not performed will be considered a missed visit.

9.8.2. 30 DAYS FOLLOW-UP VISIT: REQUIRED PROCEDURES AND EVALUATIONS

The 30 day follow-up visit shall be performed by phone. The clinical evaluation and data requirements for the registry subjects at POD 30:

- Adverse Events: Post-operative procedure or cardiac related events that resulted in medical or surgical intervention; all other serious adverse events per investigators decision using the available adverse event code list will also be collected.
- NYHA classification

9.8.3. 180 DAYS (6 MONTHS) FOLLOW-UP VISIT: REQUIRED PROCEDURES AND EVALUATIONS

The 6 month follow-up visit shall be performed at the investigational site, if applicable. The clinical evaluation and data requirements for the registry subjects at POD 180:

- Adverse Events: Post-operative procedure or cardiac related events that resulted in medical or surgical intervention all other serious adverse events per investigators decision using the available adverse event code list will also be collected.
- Medical examination: HR, BP, NYHA classification, weight
- ECG 12 lead
- Echocardiography data will be collected (if available and CD will be sent to CoreLab)
- Anticoagulation therapy
- Coagulation profile: INR and PT

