11.1. General Reporting Requirements

The EDWARDS INTIITY Elite is CE marked; therefore all adverse events should be recorded in accordance with Medical Device Directive 93/42/EEC, MEDDEV 2.12-1 Guidelines on a Medical Devices Vigilance System, ISO 14155:2011(E), and any other regulations as applicable, and as summarized in Table 2.

Adverse event reporting is an investigator's responsibility and decision. Adverse Events (AE) will be identified and captured on the AE CRF throughout the duration of the registry as they occur and will be followed until they are adequately resolved or explained.

In MISSION Registry, all Serious Adverse Events and Device/Procedure Related Events should be reported as soon as possible but no later than within 72 hours (3 calendar days) after the Investigational center first learns of the event.

All Device-Related Deaths and all Unanticipated Adverse Events (not listed in the risk section of the protocol or IFU) or Serious Device-Related Adverse Events should be reported within 24 hours after the investigational center first learns of the event.

Relevant source documents will be provided to Sponsor for evaluation and endpoints adjudication within 15 working days after the Investigational center first learns of the event. That includes source documents records from outside admissions (hospitalizations out of the enrolling site), which are related to reported adverse events/complications.

Notification to the Sponsor should be done via electronic data system by entering an adverse event into the database or if that's impossible an initial notification can be done by fax or email to the assigned Safety personnel

[contact]

In addition, investigational centers are responsible for reporting serious adverse events to their local Regulatory Bodies in accordance with the applicable requirements.

11.2. ADVERSE EVENTS COLLECTED FOR THIS REGISTRY – REGISTRY ENDPOINTS:

All Registry Endpoints and Potential Endpoints will be adjudicated (reviewed) by an independent CEC committee

TABLE 2. SAFETY ENDPOINTS DEFINITIONS

Complication	Definition
All-cause mortality	All cause mortality includes all exspirations of registry subjects as reported from investigational sites/or adjudicated per CEC

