18.1. APPENDIX A: Table of procedures and flowchart

Time Periods and Assessments	Preoperative	Operative	Discharge	30 Days (Phone)	6 Months (180 days)
Informed Consent	X				
Medical History Aortic Valve Etiology and diagnosis	X				
Inclusion Criteria / General Exclusion Criteria	X				
Medical Examination	X		X		X
Height	X				
Weight	X		X		X
Heart rate and Blood Pressure	X		X		X
NYHA	X		X	X	X
Demographics (DOB& gender)	X				
LVEF	X				
Logistic Euroscore I and II	X				
Pregnancy test (If applicable) ¹	X				
Health care utilization (Length of stay ICU and war0064)			X		

Time Periods and Assessments	Preoperative	Operative	Discharge	30 Days (Phone)	6 Months (180 days)
Implant Procedural Data and timing		X			
Intra-operative Exclusion criteria evaluation		X			
12 Lead Electrocardiogram (EKG)²	X		X		X
Transthoracic Echocardiography and Doppler	X ³		X ⁴		X ⁴
Current Anticoagulation Therapy	X		X		X
Coagulation profile: INR and PT⁵	X		X		X
Blood Studies RBC, WBC, HGB, HCT, Reticulocytes, Platelet counts, Serum Creatinine	X		X		X
Fitness for hospital discharge			X		
Quality of Life (QoL): EQ-5D SF-36	X				X
Adverse Events		X	X	X	X

1 - Pregnancy test is required for female subjects who are not post-menopausal or surgically sterile (urine)

2 - For EKG machine generated reports the Investigator must verify that the cardiac rhythm is correct and sign and date the final EKG report

3 - If available Pre-op echocardiography within 3 months of planned implant date and including echocardiographic data in the format required per the echocardiography guidelines

4 - If available echocardiography data will be collected

5 - Required only if patient is being treated with a coumadin derivation medication

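### The creatinine criterion for renal failure has no scheduled field between surgery and discharge, so counting a transient rise depends on how each site reads the adverse event rules

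*Combined protocol and SAP*

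**What the plan says.** Renal failure is one of the safety endpoints in section 7.4. Table 2 in section 11.2 introduces it as "An acute event or worsening of renal function resulting in one or more of the following", followed by two criteria. The first is "Increase of serum creatinine to >2.0 mg/dL, and 2x most recent preoperative creatinine level". The second is "A new requirement for dialysis postoperatively". Either is enough.

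Creatinine appears in the text at three visits: pre-operative (9.5), discharge (9.7) and 6 months (9.8.3). Each time the entry reads "Platelet counts, Serum Creatinine (if available per standard of care". Appendix A marks the same three columns for "Blood Studies RBC, WBC, HGB, HCT, Reticulocytes, Platelet counts, Serum Creatinine", but that row has no availability footnote, whereas the echocardiography row does. For the remaining contact, section 9.8.2 says "The 30 day follow-up visit shall be performed by phone" and lists only adverse events and NYHA class.

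Renal failure is also collected as an adverse event. Section 9.4 says "Adverse events for enrolled patients are collected from the time the subject is in the operating room", and section 11.1 adds "Adverse Events (AE) will be identified and captured on the AE CRF throughout the duration of the registry as they occur". The adverse event items in 9.7, 9.8.2 and 9.8.3 are narrower. They cover procedure or cardiac related events that led to an intervention, plus other serious events at the investigator's decision.

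**The concern.** The creatinine criterion is numerical. Applying it takes two values: the highest creatinine after surgery and the latest one before it. The schedule secures neither. The discharge value is a single reading at the end of the stay, by which time an early rise may have resolved, and the pre-operative value is conditional in the text.

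Such a case therefore reaches the database only if someone at the site recognizes it and treats it as reportable. If sites read the reporting rules differently, the early renal failure rate will partly measure reporting habits. Missed cases push it down, in the device's favour. Section 12.3 reports this endpoint as an early proportion and by Kaplan-Meier at 30 days and six months, and section 2.2 says the data will support publications and marketing information.

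**Working it through.** The plan states no expected renal failure rate, so there is no figure to reproduce. The check sets the definition against the schedule and the reporting rules.

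**1. Scheduled values against the 30-day window** (Table 1, sections 9.5 to 9.8.3, Appendix A)

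| Contact | Timing | Creatinine in text | Creatinine in Appendix A |
|---|---|---|---|
| Screening | Day -30 to -1 | conditional | listed |
| Operative | Day 0 | none | none |
| Discharge | day of discharge | conditional | listed |
| 30 days, phone | Day 23 to 37 | none | none |
| 6 months | Day 135 to 225 | conditional | listed |

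For a patient discharged within 30 days, the discharge reading is the only scheduled post-operative creatinine that can inform the early rate. The 6-month value falls at day 135 at the earliest.

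**2. Why the baseline matters**

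For a pre-operative value c in mg/dL, a peak qualifies when it exceeds 2.0 and reaches 2 × c. The absolute limit governs when c is 1.0 or less (2 × 1.0 = 2.0); above that, the doubling governs. Exclusion 12 removes screening values of 2.27 mg/dL or more. If the screening value is also the latest pre-operative one, the doubling threshold can approach 2 × 2.27 = 4.54 mg/dL. A peak between 2.0 and about 4.5 mg/dL therefore cannot be classified without c.

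**3. The adverse event route for a rise that meets the criterion and recovers without intervention**

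- Routes that include it: the synopsis says all adverse events are recorded. Section 11.4.1 counts abnormal laboratory findings as adverse events. Section 11.1 asks for serious and procedure-related events within 72 hours, with no intervention condition. Section 10.1 names the hospital chart as a primary data source. Section 11.2 sends endpoints and potential endpoints to the CEC.
- Routes that may leave it out: the visit items in 9.7, 9.8.2 and 9.8.3 require an intervention, or seriousness together with the investigator's decision. Section 11.1 also makes reporting the investigator's decision. Section 15.7 asks the principal investigator to record cardiac-related events, which a renal laboratory rise need not be.

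A rise that prolongs the stay is serious under section 11.4.3 and should be reported. The exposed case is one judged neither serious nor in need of intervention.

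**4. Later safeguards**

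No rule sends a creatinine value to the CEC. The validation programs in section 10.3 act on data in the system, so they cannot query a peak that has no field. A missing creatinine is not among the deviations in section 10.4 or Appendix E.

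**5. Size**

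With 300 subjects, one unreported case lowers the early rate by 1/300 = 0.33 percentage points. The table is an illustration only. Both the true rate and the share captured through all routes are assumed, and the captured rate is the true rate × the share captured.

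| Assumed true rate | True cases of 300 | 75% captured | 50% captured |
|---|---|---|---|
| 2% | 6 | 4.5 (1.5%) | 3 (1.0%) |
| 4% | 12 | 9 (3.0%) | 6 (2.0%) |
| 6% | 18 | 13.5 (4.5%) | 9 (3.0%) |

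**The case against.** Renal failure is a reported and adjudicated event, not a variable derived from the visit laboratory row. A rise on the second post-operative day that later resolves has a defined path: it can be read from the chart, entered on the adverse event form as it occurs, checked against source by the monitor (16.5) and reviewed by the CEC. Eligibility under exclusion 12 presupposes a screening creatinine, so the chart should usually supply a baseline. Reliance on site reporting is built into a standard-of-care registry and applies equally to hemolysis, whose laboratory markers are on no visit schedule. The endpoint is descriptive, with no planned test.

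Most of this stands. A reader might infer that an early peak which recovers is simply not recorded, or that a fixed share of cases, such as half, is lost. The documents support neither. The first overlooks the adverse event route and the dialysis criterion. The second would need incidence and recovery figures that the protocol does not give, and would have to assume that adverse event reporting finds nothing. Nor can the doubling be called impossible to compute wherever a screening value is in the chart.

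The objection does not settle whether the route works consistently. The general rules and the visit items differ in scope, and nothing specified downstream recovers a case that a site did not enter. Hemolysis shares the weakness, but creatinine is already on the schedule, so the remedy here is particularly simple.

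**Conclusion.** The point holds as a gap in ascertainment. The creatinine criterion has no scheduled in-hospital value, its baseline is conditional in section 9.5 but not in Appendix A or exclusion 12, and the visit-level adverse event items can leave out a qualifying rise that recovers without intervention. The early renal failure rate may therefore be biased low and vary with site practice across up to 30 centers.

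The size cannot be estimated from the documents. The direction rests on two assumptions: that some qualifying rises resolve before discharge, and that some sites follow the narrower visit wording. Cases meeting the dialysis criterion are unaffected, and so is the primary cross-clamp comparison. This is a worthwhile low-cost improvement to one descriptive safety endpoint, not a threat to the registry's main conclusion.

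**What to change.** - Add to the discharge form (9.7, Appendix A): highest serum creatinine between the end of surgery and discharge, with its date, transcribed from results already in the chart. The date also supplies the event time for the Kaplan-Meier estimate.
- Make the most recent pre-operative creatinine a required field, and bring section 9.5 into line with exclusion 12 and Appendix A.
- Derive the creatinine criterion by program from these two fields and send every hit to the CEC as a potential endpoint, whether or not the site reported an event.
- Beside the renal failure rate, report how many subjects have both values, so that a reader can judge completeness.

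The cost is two data fields (one of them already on the form), one programmed check and some extra adjudication. No new blood test is needed, because the peak comes from routine care and exclusion 12 already calls for the baseline. The downside is slightly more data entry and possibly a less favourable rate.
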